1 SYNOPSIS

NAME OF COMPANY Retrophin, Inc. [name] [name] USA
NAME OF FINISHED PRODUCT Not Applicable
NAME OF ACTIVE INGREDIENT Not Applicable
TITLE: An Observational, Multicenter Study of the Prevalence of Cerebrotendinous Xanthomatosis (CTX) in Patient Populations Diagnosed with Early-Onset Idiopathic Bilateral Cataracts
PROTOCOL NO.: 018CTXX15001
INVESTIGATOR STUDY SITES: This multi-center study will involve approximately 50 study sites in the United States.
OBJECTIVES: Primary Objective: To calculate the prevalence of CTX in a patient population diagnosed between the ages of 2 and 21 years old (inclusive) with early-onset idiopathic bilateral cataracts Secondary Objective: To assess other manifestations of CTX within patients presenting with idiopathic bilateral cataracts
METHODOLOGY: This is an observational, multicenter study to determine the prevalence of CTX in patient populations diagnosed with early-onset idiopathic bilateral cataracts. Patients who are potentially eligible for study participation will be identified through a chart review of patients who were seen at each study site prior to that site's initiation, or by entering care at the site while the site is participating in the trial.
NUMBER OF PATIENTS: Approximately 500 patients will be enrolled in this study.
INCLUSION/EXCLUSION CRITERIA: Inclusion Criteria: A patient must meet all of the following criteria to be eligible for this study. 
 1. The patient and/or their parent/legal guardian is willing and able to provide signed informed consent and the patient, if <18 years of age, is willing to provide assent if deemed able to do so. If the patient is ≥ 18 years of age but has diminished capacity to provide informed consent, their parent/legal guardian is willing and able to provide signed informed consent and the patient is willing to provide assent, if deemed able to do so. 2. The patient has a diagnosis of idiopathic bilateral cataracts.

NAME OF COMPANY Retrophin, Inc. [name] [name] USA
 
NAME OF FINISHED PRODUCT Not Applicable
 
NAME OF ACTIVE INGREDIENT Not Applicable

3. The patient is between the ages of 2 to 21 years old (inclusive) at the time of diagnosis with idiopathic bilateral cataracts.


Exclusion Criteria:
 
A patient who meets any of the following criteria will be excluded from this study.
 
 1. The patient has a diagnosis of cataracts with known etiology other than CTX. 2. The patient has a diagnosis of CTX. 3. The patient has cataracts caused by cataractogenic treatments. 4. The patient has taken or is currently taking cholic acid or chenodeoxycholic acid. 5. The patient has received an investigational product in an interventional clinical trial in the past 30 days. 6. The patient and/or their parent/legal guardian, in the opinion of the Investigator, is unable to adhere to the requirements of the study.

DOSE/ROUTE/REGIMEN (TEST ARTICLE): Not applicable – this is an observational study

REFERENCE TREATMENT: Not applicable

CRITERIA FOR EVALUATION: The plasma cholestanol levels and/or urine bile alcohol results (if urine sample is provided) will be used to determine whether genetic testing is indicated. Genetic testing, if indicated, will be used to determine the prevalence of CTX.

STATISTICAL METHODS:
 
Power and Sample Size: Approximately 500 patients will be enrolled in the study. Because this is an observational study, no power calculation has been performed. The study size is considered to be appropriate to investigate the prevalence of CTX among patients diagnosed or treated for early-onset idiopathic bilateral cataracts.
 
Analysis Sets: All study patients for whom results of cholestanol or urine bile alcohol testing (if urine sample is provided) are available will be included in the analysis dataset. All study patients who undergo study procedures (i.e., a blood draw) will be included in the safety dataset.
 
Demographics and Baseline Characteristics: Descriptive statistics will be used.
 
Efficacy: There are no efficacy endpoints in this descriptive, observational study.

NAME OF COMPANY

Retrophin, Inc.
[name]
[name]
USA

NAME OF FINISHED PRODUCT

Not Applicable

NAME OF ACTIVE INGREDIENT

Not Applicable

Safety:

Serious Adverse Events associated with study procedures (i.e., a blood draw) will be listed.

CTX Testing:

Plasma cholestanol levels, urine bile alcohol results (if urine sample is provided), and results of genetic testing for CTX will be summarized using descriptive statistics.

2.1 List of Abbreviations

AE	Adverse Event
CDCA	Chenodeoxycholic Acid
CTX	Cerebrotendinous Xanthomatosis
eCRF	Electronic Case Report Forms
EDC	Electronic Data Capture
FDA	The United States Food and Drug Administration
GCP	Good Clinical Practice
ICH	International Conference on Harmonization
IRB	Institutional Review Board
MedDRA	Medical Dictionary for Regulatory Activities
PI	Principal Investigator
SAE	Serious Adverse Event
SOPs	Standard Operating Procedures
US	United States
WHO	World Health Organization

3 INTRODUCTION

Genetic basis of cerebrotendinous xanthomatosis

Cerebrotendinous xanthomatosis (CTX) is a rare autosomal recessive disease caused by mutations in the cytochrome P450 *CYP27A1* gene that result in production of a defective sterol 27-hydroxylase enzyme. Physiologically, the CYP27 enzyme is present in mitochondria and involved in bile acid synthesis. If normal, it functions by introducing a hydroxyl group in the C27 position, as the first step in shortening the steroid side chain of 7 α -hydroxylated intermediates or other substrates such as cholesterol. In CTX patients, reduced bile acid synthesis causes decreased inhibition of cholesterol 7 α -hydroxylase activity and increased formation of 7 α -hydroxy-4-cholesten-3-one, which accumulates and leads to production of cholestanol and abnormal 25-hydroxylated bile alcohols.

The upregulation of both cholesterol and cholestanol synthesis leads to an accumulation of cholesterol in cholestanol-containing xanthomas in a variety of body tissues over time. This is the chief pathophysiologic mechanism responsible for many of the symptoms associated with CTX.[1]

Verrips et al [2] reported on genotypes and genotype/phenotype correlation in 58 CTX patients they studied and 67 patients reported in published literature (total of 125 patients from 74 unrelated families). Among these patients there were 37 different mutations in the *CYP27A1* gene: 16 were missense mutations; 3 were deletions; 1 was an insertion; 8 were splice site mutations; 6 were nonsense mutations; and 3 mutations were in the last nucleotides of exons. Fifteen of the 37 mutations (41%) were located in the region of exons 6-8 of the *CYP27A1* gene. Striking phenotypic heterogeneity was observed, even within families. A genotype-phenotype correlation analysis was done for 79 homozygous patients from 45 families harboring 23 different mutations, but no genotype-phenotype correlation could be established. The authors concluded that a given mutation may result in the same or different CTX phenotypes, and that mutations at different sites of the *CYP27A1* gene may likewise result in the same or different phenotypes.

Symptoms of cerebrotendinous xanthomatosis

CTX is typically a highly progressive disease, with case reports of symptoms that first appear at any time from birth through adulthood and then worsen over time. There are a wide variety of clinical symptoms and considerable morbidity in CTX patients, with disabling effects in many body systems and a high burden of illness. The most common manifestations reported are gait

disturbance, cataracts, decreased intelligence, dementia, impaired reflexes, pyramidal and cerebellar signs, dysarthria, epilepsy, neuropathy, ataxia, muscle atrophy, foot deformities, chronic diarrhea, and xanthomas, particularly of the Achilles tendon. Psychiatric, nervous system, and musculoskeletal manifestations predominate.[3, 4] The natural history of CTX has not been thoroughly studied, but case reports for several hundred patients have been published. Based on these case reports and the published review articles about CTX, the symptoms that occur earliest in children with CTX are chronic diarrhea, developmental delay, behavioral disorders, seizures, and cataracts.

Prevalence of cerebrotendinous xanthomatosis

Published articles generally state that the actual prevalence of CTX is unknown, with many patients thought to be unidentified; but the prevalence is widely assumed to be rare. Three publications have presented attempts to estimate the prevalence of CTX in specific ethnic groups.

Berginer and Abeliovich [5] noted that there had been 6 individuals from 3 Jewish families of Moroccan origin diagnosed with CTX over a 5-year period in the Beer-Sheba region of Israel. Because approximately 70,000 Jews of Moroccan origin lived in this region, the authors reported a CTX frequency of 6/70,000 for this community. Whether this represents a good estimate of prevalence for this ethnic group generally or how it compares to prevalence in other ethnic groups is not known.

Lorincz et al [6] used a genetic analysis of a CTX patient with German-English ancestry with consanguineous parents (second cousins) and her family members to estimate the prevalence of CTX. Molecular genetic analysis was performed using DNA extracted from peripheral blood leukocytes of the patient, her family members, and 115 white volunteer controls of European ancestry. The CYP27A1 exon from each sample was amplified by polymerase chain reaction. Sequencing of the amplified DNA resulted in the identification of a single homozygous substitution of thymidine for cytosine at complementary DNA position 1384 for the patient. Sequence analysis of DNA from both parents showed that they were both heterozygous, cytosine/ thymidine, at the same position. Unexpectedly, one control patient who was heterozygous for the same mutation at position 1384 was identified. Haplotype analysis of DNA from the heterozygous control patient was not performed, but there was no known familial relationship to the patient. The observed frequency of the mutation calculated for the control group was 8.7×10^{-3} . The prevalence of CTX due to this one homozygous mutation was

estimated at 1.9 per 100,000. The overall prevalence of CTX due to all known mutations was estimated to be “several-fold” higher, approximately 3 to 5 per 100,000.

Pilo-de-la-Fuente et al [7] reported on data for all patients diagnosed with CTX between 1992 and 2008 at any of the main reference centers for genetic diagnosis of CTX in Spain. CTX diagnosis was based on clinical features and mutational analysis with one exception, a patient diagnosed in 1992 for whom DNA was not available. Twenty-five CTX patients, from 19 families were identified. The authors estimated a minimum prevalence of 1/1,800,000 individuals in Spain.

Diagnosis of cerebrotendinous xanthomatosis

Suspicion of CTX is typically based on clinical symptoms, most often including chronic diarrhea with infantile onset, bilateral cataracts in children, and the appearance of xanthomas on the Achilles tendons, extensor tendons of the elbows and hands or patellar tendons, often by the third decade of life.[8] Biochemical abnormalities that indicate likely CTX are elevated bile and plasma cholestanol levels, increased ratio of serum cholestanol/cholesterol, increased urinary excretion of bile alcohol glucuronides and diminished biliary concentrations of chenodeoxycholic acid (CDCA).[9, 10] In clinical practice, elevated plasma cholestanol and urine bile alcohol are used as tests for probable CTX, with the diagnosis confirmed by a finding of mutation in the *CY 27A1* gene on chromosome 2q35-qter.[8, 11]

Treatment of cerebrotendinous xanthomatosis

CDCA has long been considered to be the standard of care for the condition. CDCA treatment is effective in preventing adverse clinical manifestations of the disease from occurring or progressing if the treatment is administered early enough.[12] Though the extent of published evidence is limited, available clinical studies and case reports suggest that the ability of CDCA treatment to reverse existing adverse clinical manifestations is mixed, with some manifestations being at least partially reversed and others stabilizing. Initiation of CDCA treatment as early as possible is universally recommended by experts, before irreversible damage has occurred.[13] There are also published reports of cholic acid being used instead of CDCA.[14, 15, 27] Recently, cholic acid has been approved for the treatment of bile acid synthesis disorders, including CTX [27].

Other treatments that have been reported to be combined with CDCA treatment in clinical practice are: Vitamin D, Vitamin E, anti-seizure medications, L-dopa-carbidopa, anti-psychotic medications, anxiolytics, anti-depressants and statins.[16-23] In a small number of reported

cases, statins were given without CDCA.[22, 24] Apheresis treatment has also reported in a small number of cases, in combination with CDCA or alone.[7, 25, 26]

Because idiopathic bilateral cataracts occur at an early age in many children with CTX, biomarker testing of these children presents an opportunity for diagnosing children with CTX. Since initiation of treatment as early as possible may prevent or reverse the development of debilitating symptoms of CTX, the opportunity to use contact with health care providers in connection with pediatric cataract evaluation and treatment is a promising avenue for disease detection and prevention.[12]

3.1 Summary of Potential Risks

This is an observational study with no drugs or treatments that could have associated risks. Drawing blood for diagnostic testing by venipuncture is an invasive procedure that may occasionally be associated with adverse events such as pain, bleeding, syncope, ecchymosis or infection.

3.2 Summary of Potential Benefits

Patients in this study will not experience personal benefits from study participation in this non-treatment, prevalence study. However, patients with CTX who are identified through participation in the study may seek medical care for CTX as a result of the diagnosis made during study participation. Study participants who test positive for CTX will be informed of the diagnosis by the Investigator and advised to seek appropriate medical evaluation and care.

4 STUDY OBJECTIVES

The primary objective of this study is to calculate the prevalence of CTX in a patient population diagnosed between the ages of 2 and 21 years old (inclusive) with early-onset idiopathic bilateral cataracts.

The secondary objective of this study is to assess other manifestations of CTX within patients presenting with idiopathic bilateral cataracts.

5 INVESTIGATIONAL PLAN**5.1 Endpoints****5.1.1 Efficacy Endpoints**

This study has no treatments and no efficacy endpoints.

5.1.2 Safety Endpoints

Only serious adverse events (SAEs) associated with study procedures (i.e., a blood draw) will be recorded.

5.1.3 Other Endpoints

CTX testing will be done using plasma cholestanol and urine bile alcohol levels (if urine sample is provided) for all study participants. Genetic testing for mutations associated with CTX will be done for all study participants with elevated plasma cholestanol levels or positive urine bile alcohol results (if urine sample is provided). Genetic testing will be performed at a Clinical Laboratory Improvement Amendment (CLIA) certified laboratory. The results of testing for plasma cholestanol and urine bile alcohol (if urine sample is provided), and genetic testing (when indicated) will be reported to the Investigator at each clinical site. The results of plasma total cholesterol (fasting or nonfasting, if > 190 mg/dL) may also be reported to the Investigator. Samples will be retained only for the duration of testing of plasma cholestanol, urine bile alcohol (if urine sample is provided), plasma total cholesterol (if applicable) and genetic testing (when indicated). Samples will not be used for future, presently unidentified research.

5.2 Study Design

This is an observational, multicenter study to determine the prevalence of CTX in patient populations diagnosed or treated for early-onset idiopathic bilateral cataracts, identified through a chart review of patients who were seen at each study site prior to that site's initiation or by entering care at the site while the site is participating in the trial.

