6.2 Exclusion Criteria

A patient who meets any of the following criteria will be excluded from this study.

1. The patient has a diagnosis of cataracts with known etiology other than CTX.
2. The patient has a diagnosis of CTX
3. The patient has cataracts caused by cataractogenic treatments.
4. The patient has taken or is currently taking cholic acid or chenodeoxycholic acid.
5. The patient has received an investigational product in an interventional clinical trial in the past 30 days.
6. The patient and/or their parent/legal guardian, in the opinion of the Investigator, is unable to adhere to the requirements of the study.

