11.5 Patient Accountability

Not applicable.

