4.1 Analysis Sets

All patients who signed the informed consent will be included in the Screened Set. All patients who signed the informed consent and whose eligibility was established will be included in the Enrolled Set. All screened patients who undergo invasive study procedures (i.e. a blood draw) will be included in the Safety Set.

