5.2 Subject Eligibility

Subject eligibility for the study (inclusion and exclusion criteria failures) will be listed for the Screened Set.

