5.3 Disposition of Patients

Patient disposition will be presented for the Screened Set. The number and percentage of patients who complete or discontinue the study, as well as the discontinuation reasons, will be provided. In addition, the number of patients who have plasma samples, urine samples, or genetic tests will be summarized.

A patient listing for study disposition will be provided for the Screened Set.

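### The prevalence estimate has no rule on which identified patients must be approached and no accounting before consent, so selection related to CTX signs could bias it in a direction the plan cannot determine

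*Protocol*

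**What the plan says.** Protocol section 4 and SAP 2.1.1 state one primary objective: to calculate the prevalence of CTX among patients diagnosed with idiopathic bilateral cataracts at ages 2 to 21.

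**Entry.** Protocol 5.2 has patients "identified through a chart review of patients who were seen at each study site prior to that site's initiation or by entering care"; this second route stays open for as long as a site takes part. The synopsis gives the same two routes: "Patients who are potentially eligible for study participation will be identified through a chart review of patients who were seen at each study site" before initiation, or entry into care afterwards. Both texts describe how patients are found. Neither says which of them must be invited, in what order, or how far back the chart review goes. Exclusion 6 in Protocol 6.2 removes a patient who, or whose guardian, "in the opinion of the Investigator, is unable to adhere to the requirements of the study".

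**Accounting.** Protocol 11.5 (Patient Accountability) reads "Not applicable". SAP 4.1 starts the count at consent: "All patients who signed the informed consent will be included in the Screened Set". SAP 5.2 adds: "Subject eligibility for the study (inclusion and exclusion criteria failures) will be listed for the Screened Set". SAP 5.3 adds: "Patient disposition will be presented for the Screened Set". SAP 5.5 summarizes the targeted medical history for the Enrolled Set.

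**Estimate.** SAP 5.7 reports five percentages with exact Clopper-Pearson 95% intervals. Criterion 4, genetically positive patients among those with a biomarker result, comes closest to the primary objective. SAP section 4 pools all summary tables across centers, and the SAP's output list has no table by site or identification route.

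**The concern.** The proportion with CTX among tested patients estimates the prevalence in the cataract population only if the chance of being approached and consenting is unrelated to CTX. Diagnosed patients are excluded, so sites cannot select on the diagnosis, but they can see signs. The introduction says "Suspicion of CTX is typically based on clinical symptoms" and names chronic diarrhea, developmental delay, behavioral disorders and seizures among the earliest in children.

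Approaching patients with suggestive charts first would breach nothing in the protocol and would push the estimate up. Passing over families of children with developmental or behavioral problems, because participation looks difficult, would push it down. The plan neither rules out these patterns nor collects what is needed to tell them apart. The Clopper-Pearson interval reflects the number tested and says nothing about how those patients were chosen.

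**Working it through.** **The plan's own figure.** The planned enrolment of about 500 cannot be reproduced. Protocol 11.2 and SAP 4.6 give no expected prevalence, precision target or power.

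**Where each stage is counted**

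| Stage | Rule or count in the plan |
|---|---|
| Identified by chart review or entering care | routes named; no count |
| Eligible among those identified | no count |
| Approached | no rule, no count |
| Declined or informally excluded before consent | no count |
| Consented (Screened Set) | counted; eligibility failures listed |
| Enrolled | counted; medical history summarized |
| Tested | counted; prevalence and interval |

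**Size if approach depended on signs.** All inputs here are assumptions; the documents give none of them.

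- p: true prevalence in the cataract pool, 1%
- f: share of the pool with CTX-like signs, 10% to 20%
- s: share of CTX cases that have such signs, 60% to 100%
- k: approach rate of CTX-like patients relative to the others

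Expected estimate: q = p × [1 + s(k − 1)] / [1 + f(k − 1)].

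- k = 2, lowest (f = 0.2, s = 0.6): 1% × 1.6/1.2 = 1.33%
- k = 2, highest (f = 0.1, s = 1): 1% × 2/1.1 = 1.82%
- k = 3, lowest (f = 0.2, s = 0.6): 1% × 2.2/1.4 = 1.57%
- k = 3, highest (f = 0.1, s = 1): 1% × 3/1.2 = 2.50%
- k = 0.5, largest shift (f = 0.1, s = 1): 1% × 0.5/0.95 = 0.53%
- k = 0.5, smallest shift (f = 0.2, s = 0.6): 1% × 0.7/0.9 = 0.78%

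The multiplier does not depend on p. Doubling multiplies any true prevalence by 1.33 to 1.82: 0.5% would become 0.67% to 0.91%, and 2% would become 2.67% to 3.64%.

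**What the interval would show.** With n = 500, five cases give a Clopper-Pearson interval of 0.33% to 2.32%. The interval contains 1% exactly when 1 to 10 cases are seen. The binomial probability of 1 to 10 cases is 98.0% when the expected estimate is 1.00%, 86.6% when it is 1.49% (inside the doubling range) and 59.6% when it is 1.98% (inside the tripling range). Nothing in the output would mark the loss.

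**The case against.** The case on the other side has real content.

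- **No evidence of selection.** A reader might infer that the protocol hands sites an open choice, or that they will favor CTX-like patients. The text supports neither. It sets no rule, and the concern stays conditional.
- **Much is visible after consent.** A reader might infer that selection cannot be seen at all. That goes too far. Protocol 8.1 makes confirming eligibility a visit procedure and requires consent before any protocol procedure, so an exclusion 6 failure after consent is listed. The Enrolled Set medical history would show a cohort unusually rich in CTX signs. What is missing is the comparison group: without data on patients not approached, a high rate of signs cannot be told apart from the true case mix.
- **Downward selection is softened.** Inclusion 1 admits patients of diminished capacity through a guardian, urine is optional, and home visits and remote consent are allowed. This makes exclusion 6 a weaker source of bias but does not remove informal exclusion before consent.
- **Accountability is not wholly absent.** SAP 5.1 to 5.3 supply set counts, disposition and sample counts. The gap lies before consent only.
- **Other documents may help.** The protocol cites a Study Operation Manual and a clinical monitoring plan, which may hold a screening log. Neither the protocol nor the SAP carries such a log into the analysis.
- **Size.** A larger figure is tempting: if a CTX patient were three times as likely to be enrolled, 1% would become 2.94%, above the 2.32% upper limit for 5 cases in 500. That assumes selection on CTX itself, whereas sites see only signs. It also sets a biased expectation against an interval from an unbiased sample. The sign-based range is the fairer illustration.

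**Conclusion.** The gap is real and bears on the primary objective. The plan sets no invitation rule and counts nobody before consent, so it can neither exclude selection related to CTX signs nor establish its direction. On the assumed inputs, the distortion is a factor of 1.33 to 1.82 if CTX-like patients are approached at twice the rate of others and 1.57 to 2.50 at three times the rate, with a corresponding fall if they are under-approached. These figures illustrate what a modest imbalance could do; they do not estimate what happened. The sponsor should act on this, because the remedy is a better sampling method for the primary estimate and not only fuller description.

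**What to change.** **Protocol 5.2.** Require each site to invite all patients who meet inclusion criteria 2 and 3, or to invite them in consecutive date order, within a look-back window that the sponsor states, regardless of CTX-associated signs.

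**Protocol 11.5.** Replace "Not applicable" with site-level counts of identified, eligible, approached and consented patients, by identification route and reason not enrolled. Where the IRB permits, add de-identified patient-level fields: age at cataract diagnosis, sex, and any CTX sign already in the chart. Recording signs for patients who have not consented raises a privacy question, so the counts should not depend on that permission.

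**SAP 5.3 and 5.7.** Add a flow from identified to tested. Beside criterion 4, show prevalence by identification route.

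**If enrolment is already complete.** The documents do not say whether it is. In that case, obtain the counts from existing site records where possible and state the limitation next to the prevalence estimate.

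**Cost.** Modest site time and one extra table. About 500 patients at about 50 sites is some 10 enrolled per site (500/50), though the counts would cover more patients than that. No study procedure is added for patients.
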